5.8 Criteria for Taking a Participant Off Study

Participants will be removed from study when any of the following criteria apply:

- Lost to follow-up
- Withdrawal of consent for data submission
- Death
- At the discretion of the investigator

The reason for taking a participant off study, and the date the participant was removed, must be documented in the case report form (CRF). In addition, the study team will ensure the participant's status is updated in OnCore in accordance with REGIST-OP-1.

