4.1 General Guidelines for DF/HCC Institutions

Institutions will register eligible participants in the Clinical Trials Management System (CTMS) OnCore. Registrations must occur prior to the initiation of any protocol-specific therapy or intervention. Any participant not registered to the protocol before protocol-specific therapy or intervention begins will be considered ineligible and registration will be denied.

An investigator will confirm eligibility criteria and a member of the study team will complete the protocol-specific eligibility checklist.

The eligibility checklist(s) and all pages of the consent form(s) will be emailed to the ODQ at [contact]. The ODQ will (a) review the eligibility checklist, (b) register the participant on the protocol, and (c) randomize the participant.

Randomization can only occur during ODQ business hours (8:30am - 5pm Eastern Time, Monday through Friday excluding holidays).

An email confirmation of the registration and/or randomization will be sent to the study coordinator(s) from the registering site, treating investigator and registering person immediately following the registration and/or randomization.

Following registration, participants may begin protocol-specific therapy and/or intervention. Issues that would cause treatment delays should be discussed with the Principal Investigator (PI) of the registering site. If the subject does not receive protocol therapy following registration, the subject must be taken off study in the CTMS (OnCore) with an appropriate date and reason entered.

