4.4 Registration Process for Other Investigative Sites

To register a participant, the following documents should be completed by the participating site and e-mailed to the Project Manager:

- Signed participant consent form
- HIPAA authorization form
- Eligibility checklist
- Screening provider note including medical/surgical history, ECOG performance status, vital signs, and physical exam findings
- Pathology report confirming pancreatic cancer (adenocarcinoma, squamous, or adenosquamous histologies)
- Laboratory reports including:
 - CBC with differential
 - Chemistry panel
 - Pregnancy test (if applicable)
 - Cardiac enzymes

- Screening imaging report (CT and/or MRI scans)
- Screening EKG
- Screening echocardiogram

To complete the registration process, the Project Manager will follow DF/HCC policy (REGIST-101) and register the participant on the protocol. The registering party will email the participant study number and assigned arm or dose treatment level to the participating site.

NOTE: Registration can only be conducted during the regular business hours of 8:30 AM to 4:30 PM Eastern Standard Time Monday through Friday, holidays excluded. Same day treatment registrations will only be accepted with prior notice and discussion with the DF/HCC Project Manager.

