5.2. Pre-Treatment Criteria

Cycle 1, Day 1, and Subsequent Cycles:

- History and physical exam with vital signs, body weight, and height (obtained within 2 weeks (14 days)).

Laboratories will be collected as follows:

- Hematological profile: CBC with differential on day 1 of each cycle
- Complete metabolic profile: Electrolytes, BUN, creatinine, liver function tests (albumin, total protein, AST, ALT, alkaline phosphatase, total bilirubin), and magnesium on day 1 of each cycle
- Tumor marker profile: CA 19-9 and CEA on day 1 of each cycle
- ANC must be ≥ 1500 for eligibility and Cycle 1 Day 1. Subsequent ANC must be ≥ 1000 .

*For all laboratory measures a window of up to 3 days prior to treatment day is acceptable.

*Baseline laboratory values obtained on Day 1 Cycle 1, with the exception of ANC as noted above, will not affect the patient's eligibility to participate in the study after the patient has undergone successful screening and randomization.

*Results must be available prior to the administration of study drug.

Imaging studies will be performed as follows:

- Chest/Abdomen/Pelvis CT scan or Chest CT scan and Abdomen/Pelvis MRI must be performed within 28 days of the date of registration. In case of CT abdomen/pelvis is used as the radiographic modality it should be protocolled specifically for evaluation of pancreas i.e. Pancreas protocol CT.

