13.6 Analysis of Secondary Endpoints

- Progression free survival time is defined as the time period from the date of randomization to the date of disease progression, recurrence after surgery or death from any cause whichever occurs first.
- The overall survival time is defined as the time duration from randomization till death or last follow-up if the patient is alive.

The distributions of overall survival and progression free survival will be estimated using the Kaplan-Meier method. Comparisons of these time-to-event endpoints by important covariate subgroups will be made using the log-rank tests. Cox proportional hazards regression models will be explored to evaluate the associations between the time-to-event endpoints and covariates of interest.

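### The off-study rules in 5.8, 4.1 and 4.3 can end PFS and OS follow-up of randomised patients once the arm is known, and nothing requires it to continue

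*Combined protocol and SAP*

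**What the plan says.** - **Leaving the study.** Section 5.8 gives four grounds: loss to follow-up, withdrawal of consent for data, death, and "At the discretion of the investigator". The last has no further criterion. The same section adds a record-keeping duty: "The reason for taking a participant off study, and the date the participant was removed, must be documented in the case report form".
- **Leaving therapy.** Section 5.6 is a separate list. It already covers a change in the patient's condition that, in the treating investigator's judgment, makes further treatment unacceptable.
- **Never starting.** Section 4.1 says "If the subject does not receive protocol therapy following registration, the subject must be taken off study", with a date and reason entered. Section 4.3 has the same rule for other sites.
- **Knowledge of the arm.** Section 5.1 states that NIS793 is not blinded. Under 4.1, "An email confirmation of the registration and/or randomization will be sent to the study coordinator(s) from the registering site, treating investigator" and the registering person. Under 4.4, "The registering party will email the participant study number and assigned arm or dose treatment level to the participating site".
- **Endpoints.** Section 13.6 says "The overall survival time is defined as the time duration from randomization till death or last follow-up if the patient is alive", and it also dates PFS from randomisation. Section 11.1.6 censors PFS at the last disease evaluation and OS at the date last known alive.
- **Follow-up.** Section 5.7 ends follow-up at new anti-neoplastic therapy, first progression or death. Section 13.2 promises active follow-up for 5 years or until progression or alternative therapy, and survival follow-up after that.
- **Populations.** Sections 13.1 and 13.7.2 define the MPR analysis set. No population is named for PFS or OS.

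**The concern.** Because 5.6 already allows therapy to be stopped on clinical judgment, the discretion ground in 5.8 adds only the power to end study participation. It stands beside death, loss to follow-up and withdrawal of consent for data, so it reads as an end to data collection. Section 6 points the same way: after the off-study visit it mentions contact only for patients with continuing toxicity, and only as an option.

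If removal tends to follow clinical decline, the patient is censored shortly before an event and the survival curve is too high. If removal or failure to start differs between arms, for example through disappointment with the control allocation, the arm comparison is affected as well. With 30 and 15 patients, one patient is 1/30 = 3.3% of Arm A and 1/15 = 6.7% of Arm B. Progression dates that were never collected are hard to reconstruct. Dates of death may be easier to obtain, but nothing in the plan asks for them.

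**Working it through.** **The plan's own figures.** The documents give no event count, power, hazard ratio or dropout figure for PFS or OS, so there is nothing to reproduce for these endpoints. The stated design figures concern MPR. Exact enumeration with 30 and 15 patients, the stated Beta priors, the 0.05 margin and the 0.74 threshold gives power 0.680 (stated 0.677) and type I error 0.157 (stated 0.162, target below 0.20). The primary design figures stand.

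**Step 1: is follow-up required after off-study status?**
- 5.8 requires a reason, a date and a status update. It requires no outcome.
- 4.1 and 4.3 require a status change with date and reason. They neither require nor forbid later collection of vital status.
- 13.2 extends survival follow-up past progression or new therapy, but does not mention patients taken off study.
- 5.7 is narrower and stops at progression or new therapy for everyone.
- 13.6 plans no sensitivity analysis for such losses.

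So the requirement is absent.

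**Step 2: what happens to never-starters?** Two readings are open. If they stay in the PFS and OS sets, they are censored at or near time zero and contribute almost nothing. If they are left out or replaced, which 13.2 suggests because its target of 45 counts patients who receive therapy, the result is exclusion after randomisation. These are different biases, and the plan does not say which applies.

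**Step 3: effect on one arm's survival curve.** Assumed: 30 Arm A patients, 15 deaths by the time point, no other censoring, and 3 of the 15 deaths censored just before they occur. True survival is 15/30 = 50%.
- First three deaths censored: their Kaplan-Meier factors multiply to 27/30, so the estimate is 0.50 / (27/30) = 55.6%.
- Last three deaths censored: their factors multiply to 15/18, so the estimate is 0.50 / (15/18) = 60.0%.

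Other positions fall between these, so the overstatement is about 6 to 10 percentage points.

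**Step 4: effect on the arm comparison.** A large-sample simulation used a true hazard ratio (A to B) of 1.0, median survival of 18 months, 30% poor-prognosis patients with hazard 2 or 3 times the rest, administrative censoring at 60 months and removal at 0 to 6 months. All of these inputs are assumed. Only poor-prognosis patients were removed.

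| Removal | Estimated OS hazard ratio |
|---|---|
| About 10% to 15% of Arm A only | 0.96 to 0.91 |
| About 10% to 15% of Arm B only | 1.04 to 1.09 |
| About 10% of both arms (hazard 2 times) | about 1.0 |

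For scale, with an assumed 35 events at 2:1, the standard error of the log hazard ratio is 1/√(35 × 2/3 × 1/3) = 0.36. The largest shift is |ln 0.914| = 0.090, and 0.090/0.36 is about one quarter of a standard error.

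**The case against.** The strongest reply has four parts.

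- **Nothing shows that the censoring would be informative.** The documents give no removal rate, reasons must be recorded, and equal removal in both arms leaves the hazard ratio near 1.0. This stands. A reader might infer that PFS and OS are biased as planned, but the text supports only that they can be. Recording a reason does not, however, recover the outcome.
- **An off-study entry in the trial management system need not stop collection of vital status.** The status may be governed by institutional policies that are cited but not reproduced. This stands in part: the protocol does not forbid such collection. It does not require it either, and followed as written it would lose the data.
- **The primary endpoint is safe, and PFS and OS are secondary with no stated power.** This largely stands. A reader might infer that the MPR result is at risk, but 13.1 counts patients who started and then went off study. Section 13.6 names log-rank tests only by covariate subgroups. Even so, objective 1.3.2 is to evaluate PFS and OS with NIS793, and Step 3 shows that a single arm's curve is affected too.
- **The 5.7 and 13.2 conflict probably touches more OS data than occasional discretionary removal.** That is plausible, and it is a reason to repair both together.

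Section 5.2 also invites a stronger reading. It says "Baseline laboratory values obtained on Day 1 Cycle 1, with the exception of ANC as noted above" do not affect eligibility after randomisation. A reader might infer that a low post-randomisation ANC ends data collection. The section says nothing about follow-up, and a pre-dose value cannot be an effect of the assigned treatment.

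**Conclusion.** The gap is real and confined to the secondary endpoints. An unblinded investigator may end a patient's study participation without a stated criterion, never-starters must be taken off study, and no section requires progression or survival follow-up afterwards, although PFS and OS are counted from randomisation. The consequence is possible prognosis- or arm-related censoring, or post-randomisation exclusion of never-starters.

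Its size cannot be stated from the documents. On the assumed inputs above, three deaths censored in Arm A raise a true 50% survival to about 56% to 60%. One-sided removal of 10% to 15%, all of poor prognosis, moves a hazard ratio of 1.0 by about 4% to 9%, which is small beside the sampling error. The case for change rests on the low cost of the repair and the difficulty of recovering missing follow-up, not on a demonstrated bias.

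**What to change.** - In 5.8, delete "At the discretion of the investigator" as an off-study ground. Section 5.6 still covers stopping therapy on judgment.
- In 4.1 and 4.3, record patients who never start as off protocol therapy.
- Keep every randomised patient, including never-starters, for survival status unless consent for data is withdrawn.
- In 13.6, state that PFS and OS are analysed in all randomised patients by assigned arm.
- Reconcile 5.7, where follow-up ends at progression or new therapy, with 13.2, which promises survival follow-up thereafter.
- In 5.2, leave the ANC criterion as it is. Add only that a post-randomisation ANC result does not end survival follow-up.

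The cost is protocol wording and a few extra survival contacts. Patients can still withdraw consent for data, so some loss related to allocation may remain. Reporting off-study reasons by arm would make it visible.

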6. DOSING DELAYS/DOSE MODIFICATIONS

Dose delays and modifications will be made as indicated in the following section. The descriptions and grading scales found in the revised NCI Common Terminology Criteria for Adverse Events (CTCAE) version 5.0 will be utilized for dose delays and dose modifications. A copy of the CTCAE version 5.0 can be downloaded from the CTEP website http://ctep.cancer.gov/protocolDevelopment/electronic_applications/ctc.htm.

If possible, symptoms should be managed symptomatically. In case of toxicity, appropriate medical treatment should be used (including anti-emetics, anti-diarrheals, etc.). All adverse events experienced by participants will be collected from the time of the first dose of study treatment, through the study and until the final study visit. Participants continuing to experience

toxicity at the off-study visit may be contacted for additional assessments until the toxicity has resolved or is deemed irreversible.

6.1 FOLFIRINOX therapy dose adjustments

Since fluorouracil, leucovorin, irinotecan, and oxaliplatin (FOLFIRINOX) are FDA approved drugs for the treatment of metastatic pancreatic cancer, subjects who experience toxicity related to FOLFIRINOX will be dose modified according to institutional standards of care at the treating investigator's discretion. Toxicities will be graded using the NCI-CTCAE Version 5.0.

If needed, dose adjustments can be reviewed with:

[name], M.B.B.S ([contact]) or [name]. ([contact]).

6.2 NIS793 therapy dose adjustments

- No dose reductions for NIS793 are allowed. In the event of treatment-related toxicity that is deemed by the investigators to be related to NIS793, NIS793 will be held until toxicity improves to Grade 1 or resolves.
- If toxicity is not attributed to chemotherapy, chemotherapy can continue per treating provider discretion. If attribution of toxicity is unclear, all treatment should be held and restarted until toxicity improves to grade 1 or resolves. In this circumstance discussion with the overall trial PI regarding restarting treatment should take place.
- If the investigator considers it to be in the participant's best interest to resume systemic chemotherapy before the toxicity has resolved to Grade 1, this may be permitted without accompanying NIS793 following documented discussion with the study PI.
- If NIS793 is held for 2 consecutive cycles it will be permanently discontinued. NIS793 would be permanently discontinued for first occurrence of certain specific toxicities detailed below. All dose interruptions or discontinuations must be based on the worst toxicity graded according to CTCAE v5.0.
- Consider early referral to specialists with expertise in the diagnosis and management of

immune related adverse events to thoroughly investigate events of uncertain etiology.

- Events not included in the study protocol should be managed as per institutional preference.

Infusion reaction or hypersensitivity reaction	Management/Next Dose for NIS793
≤ Grade 1	Decrease infusion rate until recovery from symptoms.
Grade 2	Stop infusion immediately, and keep line open. Follow institutional guidelines for the management and follow up with infusion reaction. Restart infusion at 50% of previous rate under continuous observation period ensure that there is a minimum observation period of one hour prior to restarting the infusion. If the AE recurs at the reinitiated slow rate of infusion, when despite oral premedication, then permanently discontinues that a treatment.
Grade 3 or 4	Discontinue infusion immediately, and discontinue study treatment. Provide supplemental oxygen, fluids, and other resuscitative measures as needed. Monitor vital signs (e.g. blood pressure, pulse, respiration and temperature) every 15 minutes until resolution.
Cytokine Release Syndrome (CRS)	Management/Next Dose for NIS793
Grade 2	See instructions for grade two infusion reaction above.
Grade 3 or 4	Discontinue study treatment. Follow up CRS as per institutional guidelines.

Ocular (uveitis, eye pain, blurred vision)	Management/Next Dose for NIS793
≤ Grade 1	Continue study treatment without dose modification. Ophthalmology consultation.
Grade 2	Hold NIS793. Urgent ophthalmology consultation. Upon resolution to ≤ Grade 1 may consider resuming treatment without dose reduction after discussion with study PI and in consultation with ophthalmology.
Grade 3 or 4	Discontinue study treatment. Urgent ophthalmology consultation.

Cardiovascular EKG QTc-interval prolonged; hypertension	Management/Next Dose for NIS793
Grade 3	Hold study treatment. Upon resolution to \leq Grade 1 or baseline (hypertension, QTc) or <30 msec difference from baseline (QTc) within \leq 7 days, may resume study treatment without dose modification after discussion with study PI. Baseline EKG refers to the EKG(s) collected at screening.
Grade 4	Discontinue study treatment.

Valvulopathy	Management/Next Dose for NIS793
Grade 2	Hold study treatment. Repeat echocardiogram and assess cardiac function. Once resolved to grade \leq 1 or baseline, consider re-administration of treatment, if benefit outweighs the potential risk
Grade 3 or higher	Discontinue study treatment.

Elevated cardiac enzymes (Trop I, pro NT BNP)	Management/Next Dose for NIS793
Grade 1	Continue study treatment. Consider appropriate cardiac imaging and referral to specialist.
Grade 2	Hold study treatment. Consider appropriate cardiac imaging and referral to specialist. Upon resolution to \leq Grade 1 or baseline, may resume study treatment without dose modification after discussion with study PI.
Grade 3 or higher other cardiac disorders related to study treatment.	Discontinue study drug

Other cardiovascular disorders	Management/Next Dose for NIS793

Other cardiovascular disorders	Management/Next Dose for NIS793
Grade 2 (Except myocarditis)	Hold study treatment. Upon resolution to \leq Grade 1 or baseline, may resume study treatment without dose modification after discussion with study PI. Baseline EKG refers to the EKG(s) collected at screening.
Grade 2 myocarditis Grade 3 or higher other cardiac disorders related to study treatment.	Discontinue study treatment.

AST and/or ALT elevation	Management/Next Dose for NIS793
Grade 2 AST and/or ALT	Hold study treatment. Manage per institutional practice. Upon resolution to \leq Grade 1 or baseline, consider resuming study treatment without dose modification.
Grade 2 transaminitis with bilirubin $>1.5 \times$ ULN (unless Gilbert's syndrome)	Discontinue study treatment.
Grade 3 AST and/or ALT	Hold study treatment. Manage per institutional practice. Upon resolution to \leq Grade 1 or baseline, consider resuming study treatment without dose modification after discussion with study PI. Otherwise, discontinue study treatment.
Grade 4 AST and/or ALT	Discontinue study treatment.

Isolated total bilirubin elevation	Management/Next Dose for NIS793
Grade 2	Hold study treatment. Upon resolution to \leq Grade 1 or baseline, may continue study treatment without dose modification.
Grade 3	Hold study treatment.

Isolated total bilirubin elevation	Management/Next Dose for NIS793
	Upon resolution to \leq Grade 1 or baseline, may consider resuming study treatment without dose modification after discussion with study PI. Otherwise, discontinue study treatment.
Grade 4	See footnote**. Otherwise, discontinue study treatment.
** If Grade 3 or 4 hyper-bilirubinemia is due to the indirect (non-conjugated) component only, and hemolysis as the etiology has been ruled out as per institutional guidelines (e.g., review of peripheral blood smear and haptoglobin determination), then delay study treatment until resolved \leq Grade 1, and resume study treatment at the discretion of the Investigator.	

Renal Serum creatinine	Management/Next Dose for NIS793
Grade 2	Hold study treatment. Manage per institutional practice. Upon resolution to \leq Grade 1 or baseline, consider resuming study treatment without dose modification after discussion with study PI.
Grade 3 or 4	Discontinue study treatment.

Musculoskeletal	Management/Next Dose for NIS793
Grade 2 or 3	Hold study treatment. Consider resuming study treatment without dose modification upon resolution to \leq Grade 1 with appropriate management.
Grade 4	Discontinue study treatment. In some cases, resuming study treatment may be considered after discussion with the study PI and consultation with a rheumatologist.

Dermatology (rash)	Management/Next Dose for NIS793
\leq Grade 1	Continue study treatment without dose modification. Topical steroids, antihistamines, topical emollients
Grade 2	Consider holding study treatment. Topical or oral steroids, antihistamines. If study treatment is held and resolution to \leq Grade 1,

Dermatology (rash)	Management/Next Dose for NIS793
	resume study treatment without dose modification.
Grade 3 or 4	Hold study treatment. Manage per institutional practice. After resolution to \leq Grade 1, consider resuming study treatment after discussion with the study PI.
Stevens-Johnson syndrome (SJS), or Lyell syndrome/toxic epidermal necrolysis (TEN)	Permanently discontinue study treatment.

Neutropenia	Management/Next Dose for NIS793
Grade 3 or 4	Hold study treatment. Upon resolution to \leq Grade 2 or baseline within \leq 7 days, resume study treatment without dose modification, after discussion with the study PI.

Febrile neutropenia	Management/Next Dose for NIS793
Grade 3 or 4	Hold study treatment. Upon resolution of fever and improvement of neutropenia to \leq Grade 2 or baseline, resume study treatment without dose modification, after discussion with the study PI.

Thrombocytopenia	Management/Next Dose for NIS793
Grade 3	Hold study treatment. Upon resolution to \leq Grade 2 or baseline, resume study treatment without dose modification. For Grade 3 associated with major bleeding, discontinue study treatment.
Grade 4	Discontinue study treatment.

Anemia	Management/Next Dose for NIS793

Anemia	Management/Next Dose for NIS793
Grade 3 or 4	Hold study treatment. Upon resolution to \leq Grade 2 or baseline within \leq 7 days, resume study treatment without dose modification.

Lymphopenia	Management/Next Dose for NIS793
Any grade	Treatment-related lymphopenia does not require study treatment hold or discontinuation.

Other laboratory adverse events, not specified elsewhere in table and not included in the consensus guidelines	Management/Next Dose for NIS793
Grade 3 or 4	Hold study treatment. Upon resolution to \leq Grade 1, resume study treatment without dose modification. Isolated Grade 4 electrolyte abnormalities not associated with clinical sequelae and corrected after appropriate management within 72 hours of their onset do not require discontinuation. In the case of Grade 4 electrolyte imbalances associated with clinical sequelae, or not resolved to \leq Grade 1 within 72 hours despite appropriate management, discontinue study treatment.

Other non-laboratory adverse events, not specified elsewhere in table and not included in the consensus guidelines	Management/Next Dose for NIS793
Grade 2	Consider study treatment hold, at Investigator discretion. Upon resolution to \leq Grade 1, resume study treatment without dose modification.

Other non-laboratory adverse events, not specified elsewhere in table and not included in the consensus guidelines	Management/Next Dose for NIS793
Grade 3	Hold study treatment. Upon resolution to \leq Grade 1, resuming study treatment must be discussed with the study PI.
Grade 4	Discontinue study treatment.

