Eligible patients with newly diagnosed resectable or borderline resectable pancreatic adenocarcinoma will be randomly assigned in a 2:1 allocation ratio to one of the two interventions: NIS793 and FOLFIRINOX chemotherapy for 8 cycles (Arm A, Experimental arm) followed by surgery, or FOLFIRINOX for 8 cycles (Arm B, Control arm) followed by surgery. The experimental (Arm A) and control arms (Arm B) will accrue 30 and 15 patients respectively. The first five patients randomized to NIS793 (Arm A) will be part of a safety lead-in. Study will pause until the last patient accrued for safety lead-in has completed two full treatment cycles (i.e., 28 days). Participants must have received at least 75% of their assigned doses of FOLFIRINOX and NIS793 to be considered evaluable for this safety analysis, unless dosing was held or reduced due to toxicity. If one or more of the first five participants enrolled does not meet this parameter for a reason other than toxicity (e.g. rapid disease progression and subsequent removal), Arm A will continue to accrue as many participants as needed to have five evaluable participants for safety assessment. Patients with borderline resectable pancreatic adenocarcinoma will receive chemoradiation after completion of systemic chemotherapy prior to surgery. As per the standard of care, the time interval between completion of neoadjuvant chemotherapy and radiation will be 2-4 weeks for patients with borderline resectable pancreatic adenocarcinoma and the interval between completion of neoadjuvant treatment and surgery for all patients will be between 2-8 weeks.

We will compare experimental arm to the control arm to see if it has improved the major pathological response rate (MPR). The experimental treatment will be claimed to be successful if

$\Pr(p.e > p.c + 0.05 | \text{data}) > \theta_t$, where $p.e$ and $p.c$ are the MPR for the experimental arm and control arm, respectively, and θ_t is the threshold value. We assume the prior distributions $p.e \sim \text{Beta}(0.3, 0.7)$ and $p.c \sim \text{Beta}(0.13, 0.87)$, which reflect that the expected MPR being 30% in experimental arm and 13% in control arm.

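### AST/ALT table in Section 6.2: with bilirubin above 1.5 × ULN, a Grade 2 event ends NIS793, but a Grade 3 event may be followed by resumption

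*Combined protocol and SAP*

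**What the plan says.** The AST/ALT table in Section 6.2 has four rows:

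- **Grade 2:** hold; resumption may be considered on recovery to Grade 1 or below, or to baseline.
- **"Grade 2 transaminitis with bilirubin" above 1.5 × ULN, unless Gilbert's syndrome:** stop study treatment.
- **"Grade 3 AST and/or ALT":** hold; on the same degree of recovery, "consider resuming study treatment without dose modification after discussion with study PI. Otherwise, discontinue study treatment". This row says nothing about bilirubin.
- **Grade 4:** stop study treatment.

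The bilirubin table that follows is headed "Isolated total bilirubin elevation". The general rules at the start of Section 6.2 base every interruption or discontinuation on the worst CTCAE v5.0 grade. They reserve stopping at first occurrence for toxicities listed in the tables, and they set a limit on holds: "If NIS793 is held for 2 consecutive cycles it will be permanently discontinued". Section 13.1 plans "NIS793 and FOLFIRINOX chemotherapy for 8 cycles" in Arm A.

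**The concern.** A raised bilirubin alongside raised transaminases is a more worrying signal than either alone, and the plan treats it that way at Grade 2 by removing discretion and ending NIS793. At Grade 3, with the same bilirubin, discretion returns. A site that follows the table literally could re-expose a patient to NIS793 after a liver event that would have ended the drug had it been one grade milder.

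Clear liver rules matter here because Section 2.2 states that NIS793 had not been combined with FOLFIRINOX or radiation in clinical trials. Liver test abnormalities are listed for NIS793 (Section 7.1.1) and, as very common, for irinotecan (Section 7.1.2.3).

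**Working it through.** **Step 1. Which row applies?** Take Grade 3 AST/ALT with bilirubin above 1.5 × ULN and no Gilbert's syndrome.

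| Row or table in Section 6.2 | Does it apply? | Action |
|---|---|---|
| Grade 2 AST/ALT | No, wrong grade | – |
| Grade 2 with raised bilirubin | No, label is Grade 2 only | – |
| Grade 3 AST/ALT | Yes | Hold; may resume after recovery and PI discussion |
| Grade 4 AST/ALT | No, wrong grade | – |
| Bilirubin table | No, the elevation is not isolated | – |

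The worst-grade rule also sends the event to the Grade 3 row. With this bilirubin, the sequence of actions is therefore: Grade 2 stop, Grade 3 hold with possible resumption, Grade 4 stop.

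**Step 2. Does another rule force a stop?**

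- *Hold limit (Section 6.2):* ends NIS793 only if two consecutive cycles are held. A patient who recovers sooner is not caught.
- *First-occurrence rule (Section 6.2):* covers only listed toxicities, and this combination is not listed.
- *Off-therapy criteria (Section 5.6):* unacceptable adverse events are left to judgement.
- *DLT rule (Section 13.7.1):* a related Grade 3 event counts toward stopping the arm. It does not decide whether that patient is re-dosed.

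None does.

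**Step 3. Is this pattern used elsewhere in Section 6.2?** Other tables also stop treatment for a qualified event at a lower grade, and in each the next grade up stops treatment too:

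- Thrombocytopenia: "For Grade 3 associated with major bleeding, discontinue study treatment"; Grade 4 also stops.
- Other cardiovascular disorders: Grade 2 myocarditis stops, together with "Grade 3 or higher other cardiac disorders related to study treatment".
- Infusion reactions: a recurrent Grade 2 reaction stops, as does Grade 3 or 4.

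The AST/ALT table is the exception. Section 6.2 also writes out a higher-grade range where it intends one, as the cardiovascular row shows.

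**Step 4. Size in doses.** The input is 8 planned NIS793 cycles (Section 13.1). The assumptions are that the event is found on day-1 laboratory tests of cycle k, that a held dose is not made up, and that NIS793 resumes after one held dose, the most the two-cycle limit allows.

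- Grade 2 with raised bilirubin: doses received = k − 1.
- Grade 3 with raised bilirubin: doses received = (k − 1) + (8 − k) = 7 at most.
- Difference = 7 − (k − 1) = 8 − k.

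| Event at day 1 of cycle | Grade 2 | Grade 3, up to | Difference |
|---|---|---|---|
| 2 | 1 | 7 | 6 |
| 3 | 2 | 7 | 5 |
| 4 | 3 | 7 | 4 |
| 5 | 4 | 7 | 3 |
| 6 | 5 | 7 | 2 |
| 7 | 6 | 7 | 1 |
| 8 | 7 | 7 | 0 |

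**The case against.** The strongest reply is that the Grade 3 row does not direct re-dosing. It needs a hold, recovery, and a deliberate discussion with the study PI, and it defaults to stopping otherwise. This is a real safeguard and it lowers the practical risk. It does not explain why the same discretion is withheld at Grade 2.

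The dose counts can be criticised as a best case. They assume quick recovery, agreement to resume, and delivery of every remaining dose, and they measure exposure rather than harm. That is right; they should be read only as upper bounds.

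The event may also be rare. Section 7.1.1 lists liver test abnormalities for NIS793 at fewer than 5 in 100. Applied to the 30 Arm A patients, this is fewer than 30 × 0.05 = 1.5 patients, and combined Grade 3 events are a subset. That is not a firm bound for the combination with mFOLFIRINOX, which brings its own liver effects.

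Intent is inferred. A Grade 2-only rule could have been meant literally, or a symbol could have been lost when the PDF was read. The second cannot be excluded, but other inequality signs survive in the same table and nothing in the text shows a loss. As for the first, the plan gives no reason for being stricter at the lower grade.

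**Conclusion.** The concern holds. As written, Section 6.2 requires permanent discontinuation for Grade 2 AST/ALT elevation with bilirubin above 1.5 × ULN and allows resumption for Grade 3 with the same bilirubin. The conclusion rests on the row labels and on the absence of any overriding rule, not on the dose arithmetic. Under the stated assumptions, the difference in permitted NIS793 exposure runs from up to 6 doses for an event at cycle 2 to none at cycle 8. How many patients would be affected cannot be derived from the documents. No endpoint, power or type I error figure changes. It should be fixed because it is a safety instruction that runs in the wrong direction.

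**What to change.** Amend three row labels in the AST/ALT table:

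1. Combined row: *Grade 2 or higher AST and/or ALT with bilirubin >1.5 × ULN (unless Gilbert's syndrome)*, with the action unchanged (stop).
2. Plain Grade 2 row: add *with bilirubin at or below 1.5 × ULN, or Gilbert's syndrome*.
3. Plain Grade 3 row: add the same limit.

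Leave the Grade 4 row as it is. If the sponsor does intend to allow resumption at Grade 3, it should state why Grade 2 is stricter.

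No new tests are needed, since Section 5.2 already has AST, ALT and total bilirubin drawn on day 1 of each cycle. The cost is an amendment, and a few Grade 3 patients who recover and might have resumed will lose NIS793. They can continue mFOLFIRINOX on the conditions in Section 6.2: freely if the toxicity is not attributed to chemotherapy, but with all treatment held first if attribution is unclear. Attribution may well be unclear, because irinotecan and oxaliplatin have liver effects of their own. Biliary stents and drains are permitted (Section 3.1.3), so it is worth keeping clear that the row, like the opening rule of Section 6.2, concerns toxicity judged related to NIS793.
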